4.1. Trial setting

This is a single centre trial at the University Hospital of Wales (UHW), Intensive Care Unit (ICU). UHW is a tertiary referral centre hospital and has a 1000 bed capacity. The ICU is funded for 36 adult critical care beds and accepts patients requiring level 2 and level 3 care. This selected site has the capacity to manage level three care, with a patient population who are likely to require prolonged intubation and ventilation.

The ICU has access to a specialised Critical Care Research Team who provide 24-hour care for research participants in the ICU. The team facilitate 24-hour recruitment into critical care research studies whilst also providing full time advice and management for research participants. At UHW the ICU Consultants provide 24-hour residential cover, whereby participants are under the constant care and supervision of a fully qualified Critical Care specialist consultant.

At UHW the pathways of recruitment will be via the Accident and Emergency Department, deteriorating patients from the hospital wards, or deteriorating level 2 patients within ICU.

5. Participant eligibility criteria

5.1. Inclusion criteria

- >18 years old (no upper age)
- Patient required endotracheal intubation
- Expect to remain intubated for 24 hours post randomisation

5.2. Exclusion criteria

- The person intubating the patient assesses that the patient has already aspirated.
- GCS 7 or less on presentation to hospital
- Patient is pregnant
- Patient has tracheostomy
- Patient has gastrectomy
- Patients who have been intubated prior to arrival at hospital
- Patients who are already endotracheally intubated and require a tube change.

6. Trial procedures

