6.1.2. Screening

The patient will be screened using the predefined study inclusion and exclusion criteria. Screening will be carried out by the airway practitioner intubating the patient, ICU medical staff who are part of the intubation team, ODP's, or critical care research specialist nurses, who are all part of the clinical care team. Screening of participants will take place at the bedside of patients requiring intubation for critical illness. This patient population are likely of low consciousness or physiologically obtunded. Therefore, information will be gathered primarily from accessible patient medical notes along with any relevant verbal history from the doctors and nurses responsible for the patients' clinical care.

Once the patient has been screened using the inclusion and exclusion criteria, eligibility for inclusion into the study will be confirmed by the airway practitioner intubating the patient, ICU medical staff who are part of the intubation team, ODPs, or critical care research specialist nurses. This information will be collected on a data collection document that will be kept with the Standard Operating Procedure Checklist that is used during an intubation procedure and then returned to the critical care research team. Training specific to this study will be provided to those who will be delegated the task of screening and confirming eligibility.

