6.1.4. Consent

Patients who require rapid intubation due to the nature of their critical illness are likely to be of a low consciousness level or significantly physiologically obtunded and as such there will not be time to obtain informed consent from patients. Therefore, an emergency deferred consent model will be used for this study. This complies with the legal requirements for obtaining consent in patients without capacity in England and Wales (Mental Capacity Act 2005) and GCP guidelines.

The two ETTs that are being used in this study are CE marked medical devices used within their intended purpose so randomisation will occur following confirmation of eligibility for inclusion into the study. The allocated ETT will be sited. Advice will then be sought from a Personal Consultee, or if they are unavailable, a Nominated Consultee, as to what they believe the patients' wishes would be with regards to ongoing study participation.

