6.1.8. Additional consent provisions

No data or biological specimens will be acquired, transferred or stored during the trial for use in ancillary studies.

6.2. Randomisation.

In order that randomisation does not delay immediate intubation in any way, the use of remote randomisation is dismissed.

Randomisation will be via a sealed randomised sequence envelope approach. Simple randomisation will be used and will be conducted via a computer generator. Allocation will be based on a 1:1 allocation ratio.

In order to prevent bias or tampering:

- 1. Envelopes will be sequentially numbered, opaque, sealed and stapled.
- 2. The allocation sequence will be concealed from staff who are involved in delivery of the study and from healthcare professionals involved with confirming eligibility for the study.
- 3. Envelopes will be prepared off-site by Cedar staff who are not involved in the design or conduct of this study.
- 4. The person preparing the envelope will sign the back, and a foil insert will be used to prevent transillumination.

5. To prevent subversion of the allocation sequence, the name and date of birth of the participant will be written on the envelope prior to it being opened.

Logistically, sealed envelopes will be available to intubation teams in two locations. One site within Intensive Care for all in-departmental intubations. The second attached to the ward intubation kit bag, which will attend all ward intubations. Once an envelope has been used the envelopes will be replaced by the research team in sequence until all envelopes are utilised. The box of envelopes will be held securely in a locked cupboard at the Critical Care research office.

Upon allocation the intubation team will prepare the allocated endotracheal tube as part of the standard intubation kit.

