6.3. Blinding

Due to the nature of the interventional device it is not possible to blind the care providers or outcome assessors to the intervention group. The trial participants will be unconscious/sedated for the duration of the period that the PneuX device or standard ETT is in place and therefore will be unaware of their allocation. Samples sent to RD Biomed laboratory for analysis will be anonymised using individual deidentified numbers for each participant.

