6.7. Withdrawal criteria

Each participant has the right to withdraw from the study at any time. In addition, the CI may withdraw a participant from the study at any time if the CI considers it necessary for any reason including:

- Ineligibility (either arising during the study or if, during the study, previously unknown issues come to light which would make the participant ineligible)
- Significant protocol deviation as decided by the CI
- Significant non-compliance with treatment regimen or study requirements
- Withdrawal of consent by the patient or consultee (patients' study data up to the point of withdrawal will be kept).

Daily data collection will cease if:

- The patient has been extubated in the first 24 hours following intubation
- Planned extubation (the patient has improved, or the tube required changing for clinical reasons)
- Un-planned extubation (accidental removal of the tube)
- The patient has died with the tracheal tube still in place
- The patient has had a tracheostomy.

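### The aspiration exclusion has no time point, and Section 6.7 allows withdrawal for ineligibility found after the arm is known, so per-arm pepsin rates could be selectively altered

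*Protocol*

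**What the plan says.** **The criterion.** Section 5.2 lists as an exclusion: "The person intubating the patient assesses that the patient has already aspirated". It names who judges, but gives neither a time point nor a definition.

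**Who confirms eligibility.** Under Section 6.1.2, "eligibility for inclusion into the study will be confirmed by the airway practitioner intubating the patient, ICU medical staff" in the intubation team, ODPs or research nurses. Information comes mainly from the notes and from verbal history.

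**Order of steps.** Section 6.1.4 states that "randomisation will occur following confirmation of eligibility for inclusion into the study". Section 6.2 adds two protections: "The allocation sequence will be concealed from staff who are involved in delivery of the study" and from those confirming eligibility, and "the name and date of birth of the participant will be written on the envelope prior to it being opened". Then: "Upon allocation the intubation team will prepare the allocated endotracheal tube as part of the standard intubation kit".

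**Blinding.** Section 6.3 says "it is not possible to blind the care providers or outcome assessors to the intervention group".

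**Removal after randomisation.** Section 6.7 lets the chief investigator withdraw a participant at any time. One listed reason is "Ineligibility (either arising during the study or if, during the study, previously unknown issues come to light which would make the participant ineligible".

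**Outcome and analysis.** The pepsin-positive rate in both arms is a main outcome (Sections 3.3, 3.5 and 6.5.1). Section 9.3 reports it as frequencies and rules out between-group comparisons.

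**The concern.** The criterion is subjective and closely related to what the pepsin test detects. It is also assigned to the person who will place the allocated tube. If the judgement is made, or revised, after the envelope is opened, that person knows the arm.

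A patient removed at that stage is more likely than average to be pepsin-positive, because Section 6.5 schedules tracheal and subglottic sampling from day 0. Removal would therefore tend to lower the observed positive rate. If the readiness to report aspiration depended on which tube was in hand, the rate would fall by different amounts in the two arms.

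At stake are the descriptive per-arm rates. Sections 3.2 and 9.1 say that the data are to inform later studies. A removal rule left loose here could also be carried into the full RCT, where it would affect a formal comparison.

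**Working it through.** The plan gives no figure on this point, so there is none to reproduce. The check is mainly of sequence.

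**Step 1. Intended order.** Screen (6.1.2), confirm eligibility, randomise (6.1.4), open the named envelope and prepare the allocated tube (6.2), site the tube (6.1.4). Aspiration is an eligibility criterion, so this order covers it. A judgement made in this order is blind to arm.

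**Step 2. Is the intubator's judgement guaranteed to come before opening?** No. Section 5.2 assigns it to the intubator, while Section 6.1.2 allows an ODP or research nurse to confirm eligibility. No step requires the intubator's judgement to be written down first. Two details blur the boundary further. Section 6.1.2 keeps the eligibility form with a checklist used during the intubation procedure. Section 6.4 describes the airway practitioner's assessment as part of screening, yet its items include tube position at the teeth, known only once the tube is in. Section 6.1.1 adds that intubation teams may not have GCP training, so unwritten convention is a weak safeguard.

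**Step 3. What if aspiration is recognised after opening?** It is then seen with the arm known (6.2, 6.3). It fits the Section 6.7 wording on previously unknown issues. The decision is the chief investigator's, but it would rest on the unblinded report. Section 6.7 says that data up to withdrawal are kept only in the item on withdrawal of consent, and is silent for ineligibility. No section says that such a patient stays in data collection or is reported in the randomised arm.

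**Step 4. Illustration of size.** Assumptions: 25 patients per arm (Section 4), the same true patient-level positive rate *p* in both arms, and *k* pepsin-positive patients removed from one arm only. The range for *p* borrows the 50–75% microaspiration figure in Section 1.2, with 60% as a value in between. That figure is not a Peptest positivity rate. The values of *k* are assumed.

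Observed rate in the affected arm = (25*p* − *k*) / (25 − *k*). Standard error of one arm's rate = √[*p*(1 − *p*)/25].

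| *p* | *k* = 1 | *k* = 3 | *k* = 5 | SE of one arm |
|---|---|---|---|---|
| 50% | 11.5/24 = 47.9% (−2.1) | 9.5/22 = 43.2% (−6.8) | 7.5/20 = 37.5% (−12.5) | 10.0 points |
| 60% | 14/24 = 58.3% (−1.7) | 12/22 = 54.5% (−5.5) | 10/20 = 50.0% (−10.0) | 9.8 points |
| 75% | 17.75/24 = 74.0% (−1.0) | 15.75/22 = 71.6% (−3.4) | 13.75/20 = 68.75% (−6.25) | 8.7 points |

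Values in brackets are the shift in percentage points, which is also the spurious gap from the untouched arm. One to three removals give shifts below one arm's standard error. Five give a shift of about that size. The outcome in Section 3.5 counts samples, taken daily to day 7, so these patient-level figures show direction and rough scale only.

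**The case against.** The strongest reply is that the protocol already fixes the order. Eligibility is confirmed before randomisation, the sequence is concealed from those confirming it, and a screening checklist travels with the envelope (6.1.1). **This stands.** A reader might infer that the exclusion itself is made by someone who knows the arm. The documents do not support that. They leave open only what happens when aspiration is recognised after opening.

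Other objections also stand, in whole or in part:

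- **Who removes the patient.** A reader might infer that the intubator can drop a patient. Under Section 6.7 the chief investigator decides.
- **When aspiration is seen.** That it may first be seen at laryngoscopy is a reasonable clinical inference. The protocol does not say so and gives no frequency.
- **Recruitment count.** A reader might infer that the count of 50 becomes unreliable. Numbers screened, consented and randomised are logged with reasons for withdrawal (3.5), the envelope is named before opening (6.2), reasons for randomisation failure are tabulated (9.3) and CONSORT reporting is promised (12). A removal would leave a trace.
- **Comparison.** No hypothesis is tested (3.1) and no between-group comparison is planned (9.3), so no test is biased.
- **Pre-tube aspiration is a contaminant.** Excluding it before randomisation is sensible, because the later question concerns microaspiration in ventilated patients. This does not justify removal after the arm is known, but it does support showing pepsin rates both ways.
- **Analysis populations belong in the SAP, which is not shown.** True. But the withdrawal rule is in the protocol, and an analysis rule cannot restore data that were not collected.

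**Conclusion.** The point holds in limited form. The protocol intends a concealed eligibility decision, but does not ensure that the intubator's aspiration judgement is recorded before the envelope is opened. It also provides a route to withdraw a patient on an unblinded report of aspiration, with nothing that keeps the patient in follow-up or in the arm's results.

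The consequence is a possible selective change in the per-arm pepsin-positive rates, a main descriptive outcome. Its size is unknown. It is likely to lie within one arm's standard error, about 10 points with 25 patients, unless removals are several and one-sided. This rests on two assumptions that the documents neither confirm nor exclude: that aspiration is sometimes first recognised after opening, and that Section 6.7 would then be used.

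The change is worth making because it costs almost nothing and the rule may be carried into the RCT.

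**What to change.** - **Sections 5.2 and 6.1.2:** state that the intubator's aspiration judgement is made on what is known at that time and is recorded on the existing screening checklist before the envelope is opened.
- **Section 6.4:** record aspiration first recognised after opening as a baseline item (yes/no, with time).
- **Section 6.7:** state that such a finding is not a ground for withdrawal from the study. The patient stays in data collection and is reported, flagged, in the randomised arm. Limit the change to this point. Deleting the ineligibility clause altogether would affect every other criterion, such as pregnancy or gastrectomy, to solve a problem with one.
- **Section 9.3:** show the pepsin rates by arm with and without the flagged patients.

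The cost is a few sentences, one checklist entry and one extra descriptive row. The downside is small: a few patients with aspiration before the tube was placed stay in the data, so the main positivity rates may be slightly higher. The second set of rates shows by how much.

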6.1. Recruitment

Sponsor reference: 21/NOV/8290

The patient population for this study are those who are experiencing critical illness requiring intubation and ventilatory support. Patients meeting these criteria will be level 2 patients that are already being cared for within the ICU or patients on the wards who are referred to the ICU team via formal referral from the medics responsible for the patients' care, the Emergency Resuscitation Team, or the Patient at Risk Team (PART). At the point that a decision to intubate the patient is made via these teams, an intubation team will be called and the patient will become eligible for screening against the study inclusion and exclusion criteria.

6.1.1. Participant identification

Identification of patients will be via intubation teams. Each intubation team called to intubate patients on the wards will include a trained airway practitioner who will intubate the patient and an Operating Department Practitioner (ODP) who will assist. Within the ICU the intubation team will consist of trained airway practitioners who will intubate the patient, with medical and nursing staff who will assist. Whilst these staff may not have received Research Good Clinical Practice (GCP) training, trained research staff will have ensured that:

- All intubation teams likely to encounter potential participants are aware of the study, its inclusion criteria and protocols
- All of the medical and nursing staff in the ICU are aware of the study, its inclusion criteria and protocols
- All relevant departments are aware of the study, its inclusion criteria and protocols, through presentations at departmental meetings
- All relevant materials to conduct the study will be available prior to the intubation. Specifically, the intubation teams will have a screening checklist, randomisation envelope, and endotracheal tubes for each arm of the study in a variety of various sizes ready.
- For patients being intubated on the wards the study materials will be transported to the patient in the emergency airway bags that the intubation team take to each intubation as standard practice. For patients in the ICU the study materials will be kept with the 'Difficult Airway Trolley' that is made available for all intubations.

6.1.2. Screening

The patient will be screened using the predefined study inclusion and exclusion criteria. Screening will be carried out by the airway practitioner intubating the patient, ICU medical staff who are part of the intubation team, ODP's, or critical care research specialist nurses, who are all part of the clinical care team. Screening of participants will take place at the bedside of patients requiring intubation for critical illness. This patient population are likely of low consciousness or physiologically obtunded. Therefore, information will be gathered primarily from accessible patient medical notes along with any relevant verbal history from the doctors and nurses responsible for the patients' clinical care.

Once the patient has been screened using the inclusion and exclusion criteria, eligibility for inclusion into the study will be confirmed by the airway practitioner intubating the patient, ICU medical staff who are part of the intubation team, ODPs, or critical care research specialist nurses. This information will be collected on a data collection document that will be kept with the Standard Operating Procedure Checklist that is used during an intubation procedure and then returned to the critical care research team. Training specific to this study will be provided to those who will be delegated the task of screening and confirming eligibility.

6.1.3. Payment

No payments will be offered to trial participants.

6.1.4. Consent

Patients who require rapid intubation due to the nature of their critical illness are likely to be of a low consciousness level or significantly physiologically obtunded and as such there will not be time to obtain informed consent from patients. Therefore, an emergency deferred consent model will be used for this study. This complies with the legal requirements for obtaining consent in patients without capacity in England and Wales (Mental Capacity Act 2005) and GCP guidelines.

The two ETTs that are being used in this study are CE marked medical devices used within their intended purpose so randomisation will occur following confirmation of eligibility for inclusion into the study. The allocated ETT will be sited. Advice will then be sought from a Personal Consultee, or if they are unavailable, a Nominated Consultee, as to what they believe the patients' wishes would be with regards to ongoing study participation.

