We propose a full randomised controlled trial (RCT) to address the question of whether the PneuX device reduces the microaspiration of pepsin, and the impact of several secondary outcomes, including VAP rate. Before a full-scale RCT can be done, **we propose this feasibility study using 50 patients to be undertaken**. This will help to identify the intervention fidelity – the extent of which the intervention can be delivered as intended and will help to reveal any problems or obstacles related to implementation of the study. Any problems identified can then be remedied to ensure methodological rigour and scientific validity in the full-scale RCT. The feasibility study will establish the acceptability of the randomisation procedure by clinicians. Similarly, the willingness of patients to participate in the study and the appetite for clinicians to recruit participants will need to be ascertained.

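### The entry criteria do not require loss of capacity, yet the only entry route is deferred consent, whose stated legal basis covers only patients without capacity

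*Protocol*

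**What the plan says.** Section 5.1 has three inclusion criteria: age over 18, "Patient required endotracheal intubation" and "Expect to remain intubated for 24 hours post randomisation". Section 5.2 lists seven exclusions, none of which concerns capacity to consent.

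Under Section 6.1, screening opens once a decision to intubate has been made. The source population includes referred ward patients and "level 2 patients that are already being cared for within the ICU".

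Section 6.1.4 gives two reasons for deferred consent. Patients needing rapid intubation "are likely to be of a low consciousness level or significantly physiologically obtunded", and "there will not be time to obtain informed consent from patients". It adopts the deferred model for the study as a whole and adds the compliance statement: "This complies with the legal requirements for obtaining consent in patients without capacity in England and Wales". Randomisation then follows confirmation of eligibility, the allocated tube is sited, and advice is sought from a Personal Consultee or, failing that, a Nominated Consultee. Under Section 6.1.7 the patient is approached once capacity has been regained.

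Section 2 (Rationale) adds that "the willingness of patients to participate in the study and the appetite for clinicians to recruit participants will need to be ascertained".

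**The concern.** The consent model and the entry criteria describe different populations. Section 6.1.4 reasons from patients who cannot be asked. Section 5.1 admits any adult who needs intubation and is expected to stay intubated for 24 hours. If some of those patients can be asked, the plan gives staff no instruction to do so and no route by which the patient could agree or refuse before allocation.

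Two things are at stake. First, participation of an eligible patient with capacity would rest on a statement that does not cover that patient, which leaves the enrolment open to challenge. Second, one purpose of this feasibility study is to learn about willingness to take part. Under the present text willingness is recorded only after allocation, including for any patient who could have answered beforehand. A later, larger trial would probably inherit the same consent model.

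**Working it through.** The point is not numerical, and the protocol gives no figure to reproduce. The check sets the sections side by side.

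1. **Who is eligible (5.1, 5.2).** The inclusion criteria cover age, need for intubation and expected duration. The exclusions cover suspected aspiration already, GCS at presentation, pregnancy, tracheostomy, gastrectomy, intubation before arrival, and tube change. None refers to capacity at the decision to intubate. None requires that intubation be so urgent that the patient cannot be asked.

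2. **Does the protocol treat incapacity as universal?** No. Sections 6.1.2 and 6.1.4 both use the word *likely*. That describes what is expected and does not limit entry.

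3. **What triggers randomisation (6.1.4)?** Confirmed eligibility, with no further condition. Section 6.1.2 has eligibility confirmed mainly from the notes and from staff, and describes no capacity assessment.

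4. **What does the compliance statement cover?** Patients without capacity. Lack of time is offered as a reason for deferral, but the compliance sentence is not worded to include a patient who has capacity and for whom time is short.

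5. **Does another section close the gap?** Sections 6.1.5 and 6.1.6 concern consultees. Section 6.1.7 approaches the patient once capacity is regained, so it presumes earlier loss. Section 6.1.8 concerns ancillary studies. The assessments table in 6.5 has a consent row that seems to fall on day 0, but the table text is broken, and 6.1.4 places consultee advice after the tube is sited.

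| Patient at the decision to intubate | Eligible under 5.1/5.2? | Asked before allocation under 6.1.4? | Covered by the compliance sentence? |
|---|---|---|---|
| Lacks capacity | Yes | No | Yes |
| Has capacity, time short | Yes | No | No |
| Has capacity, time available | Yes | No | No |

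Eligible here means that the other criteria are met. The last two rows are the contradiction: the criteria admit them and the stated consent basis leaves them out.

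**Size.** The share of eligible patients in the last two rows is not given and cannot be derived from the protocol. Each such patient would be 1/50 = 2% of the planned sample.

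**The case against.** The best reply is that the trial's setting makes the gap small. Section 4.1 speaks of deteriorating patients, Section 6.1 of critical illness and an intubation team being called, and Section 6.2 of randomisation that must not delay immediate intubation. Section 6.1.4 names lack of time as a ground in its own right. By the time a consultee is approached, participants are sedated or unconscious (6.3), so the gap is confined to the randomisation step. The screening checklist (6.1.2, 6.1.1) and the study-specific training are not shown and may include a capacity check.

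Most of this stands as context. It makes patients with capacity probably uncommon and narrows the problem to one step. It does not remove the problem, because a description of setting is not an eligibility rule, and the protocol is the document that fixes who may be randomised.

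A reader might infer more than the documents support:

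- *That excluding patients by "GCS 7 or less on presentation to hospital" selects alert patients.* The score is taken at presentation. Ward and ICU patients may have deteriorated since, so it says little about capacity at randomisation.
- *That a particular share of participants has capacity.* Nothing in the protocol anchors a percentage.
- *That this gap causes loss of samples after allocation is known.* Section 6.8 destroys samples on refusal or withdrawal for every participant. That is a feature of deferred consent generally and would remain after the fix. Section 9.3 plans no between-group comparison.
- *That patients are never asked.* Section 6.1.7 seeks their consent when capacity returns, and Section 3.5 logs numbers consented and reasons for non-consent. Willingness is measured, but only after allocation.

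**Conclusion.** The eligibility criteria and the consent section do not match. Following the protocol exactly, an eligible patient who has capacity at the decision to intubate could be randomised and intubated with the allocated tube without being asked, outside the consent basis that Section 6.1.4 states. This goes beyond missing detail, because eligibility alone triggers randomisation and the compliance statement is limited to a narrower group.

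The number affected is unknown and may be small. The conclusion rests on the text of 5.1, 5.2, 6.1.2 and 6.1.4 to 6.1.8, and on one assumption: that no unseen checklist or training material adds a capacity condition. If one does, the remedy is simply to bring it into the protocol.

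A reader might go further and conclude that the study breaches the law on consent. The protocol does not allow that conclusion: the statute and guidelines it cites are not reproduced, and the point is one of internal consistency. The two sections should be reconciled before recruitment, and the change is cheap.

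**What to change.** Add to Section 5.1 and to the screening checklist an item that the patient lacks capacity to consent at the time of the decision to intubate, recorded yes or no by the screening clinician before the envelope is opened. Section 6.1.2 lets several roles screen, so it should say which of them may make this judgement.

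Limit Section 6.1.4 to patients recorded as lacking capacity. For those with capacity, choose one course and write it down: make them ineligible, or set out a prior-agreement route to be completed before allocation. Whether a given form of prior agreement is sufficient is for the sponsor and the ethics committee to settle. Log capacity status and any refusal in the screening data, so that willingness before allocation is also observed where it can be.

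The cost is one criterion, one checklist item and a short amendment to 6.1.4. In use it is one extra tick at an emergency procedure, which must be kept brief enough to respect the aim in Section 6.2 that intubation is not delayed. Recruitment may be slightly lower if patients with capacity are excluded or decline. The size of that loss cannot be estimated from the protocol, and the log would show it.
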